Protocol Title

Multi-center, 6-month, randomized, and controlled trial to compare the effects of Myo Munchee therapy and Oral Motor Therapy (OMT) in pediatric patients (aged 3-5 years) to treat maxillary deficiency and orofacial myofunctional dysfunction (OMD).

General Information

Protocol Title			
Multi-center, 6-month, randomized, controlled trial to compare the effects of Myo Munchee therapy and Oral Motor Therapy (OMT) in pediatric patients (aged 3-5 years) to treat maxillary deficiency and orofacial myofunctional dysfunction (OMD).			
Protocol identifying number	0001		
Version Number	27	Version date	25/04/2025
Clinical Trial Sponsor			
Sponsor Name	Myo Munchee		
Sponsor Contact			
Telephone			
Email	[contact]		
Address	[name]		
Principal Investigator			
Name			
Telephone			
Email	[contact]		
Personnel authorized to sign the protocol and the protocol amendment(s) for the Sponsor (ICH GCP 6.1.3)			
Name			
Telephone			
Email	[contact]		
Address	[name]		
Independent Review Board			

Name	Allendale Investigational Review Board
Status of ethical review	 Approved  In progress  To be submitted
Trial Sites	1. [name] 2. [name]
Funding for the Clinical Trial	
Funding Body Name	Myo Munchee (Operations) Pty Ltd

Safety and Monitoring Contacts

Clinical Trials Involving Investigational Medical Device	
Study Coordinator and Principal Investigator - remote	
Name	
Telephone	
Email	[contact]
Address	[name]
Study Coordinator - Chicago	
Name	
Email	

Introduction and Hypothesis

In combination, or as a sole disease entity, when Skeletal Malocclusion (SM), Orofacial Myofunctional Dysfunction (OMD), Sleep Disordered Breathing (SDB) and/or Tethered Oral Tissue (TOT) traits are present in Early Childhood (before the age of 72 months old), a young child's quality of life and general health status may be compromised.

Over a period of six months, when SM, OMD, SDB and/or TOT traits are individually, or in some combination, present in early childhood, Oral Motor Therapy (OMT) with, or without, adjunctive intervention with Myo Munchee Therapy (MMT), will result in improved SM, OMD, SDB and/or TOT trait co-morbidities.

Purpose

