To evaluate the effectiveness of three different treatment options, either as sole interventions, or as adjunctive intervention strategies, for mitigating symptoms often associated with SM, OMD, SDB and/or TOT phenotypes when initially detected under the age of 72 months old.

Outcomes and objectives

For each child enrolled in the study, the outcomes below are desired.

- 1. Primary outcomes**
 1. Palatal transverse width expansion
 2. Palatal sagittal depth expansion
 3. Palatal vault height expansion
- 2. Secondary outcomes**
 1. OMD resolution
 2. Improvement in sleep and behavior
- 3. Study objectives are intended for the practitioner community**

Eligibility Criteria, Materials and Methods

Eligibility criteria

Inclusion Selection Criteria:

1. Aged between 36 - 60 (3-5 yrs) months old and will not turn 6 years of age before the study completion
2. Diagnosed with having at **least two** maxillary skeletal-dental malocclusion traits as determined by the measurements below
 - a. Palatal transverse (width), detailed measurement information described in methods section
 - i. Anterior inter-canine width (Thilander study [link](#))
 1. Male: age range (4.7-5.55 years); range 26.8-32.8mm, average = 30.5mm. If patient is below 26.8mm, eligible for study
 2. Female: age range (4.6 - 5.2 years); range 25.6-32.3mm, average = 28.4mm. If patient below 25.6mm, eligible for study
 - ii. Posterior inter-molar width (Bogue index, 24mm + age) measurement for both male and female
 1. 3-year-old: and less than 27mm (posterior)
 2. 4-year-old: and less than 28mm (posterior)
 3. 5-year-old: and less than 29mm (posterior)
 - b. Palatal sagittal depth/length (Thilander study [link](#))
 - i. Second deciduous molar (from distal alveolar crest to incisive papilla):

1. Male: age range (4.7-5.55 years); range 22.0-28.5mm, average = 25.1mm. If patient below 22mm, then eligible for study.
2. Female: age range (4.6 - 5.2 years); range 18.0-25.0mm, average = 21.4mm. If patient below 18.0mm, eligible for study.
- c. Palatal vault height (Thilander study [link](#))
 - i. Second deciduous inter-molar height (measured from the center of the line connecting the disto-gingival margins of the 2nd molars (at alveolar crests) down to the contact with the mid-palatal suture):
 1. Male: age range (4.7-5.55 years); height range: 12.5-17.0mm, average = 14.2mm. If patient below 12.5mm, eligible for study

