 - i. Boys: <https://www.cdc.gov/growthcharts/data/extended-bmi/BMI-Age-percentiles-BOYS-Z-Scores.pdf>
 - ii. Girls: <https://www.cdc.gov/growthcharts/data/extended-bmi/BMI-Age-percentiles-GIRLS-Z-Scores.pdf>
6. History of prescription for therapeutic gum chewing and/or use of edibles in treatment program
7. Previous tongue tie releases (frenuloplasty and frenectomy)
8. Any therapeutic oral device treatment
9. Previous or current treatment from any other dental, OMT or orthodontic provider
10. Gross neglect of patient's oral health and presence of dental caries
11. Grade 4 tonsils on Brodsky scale

Screening Criteria

1. Accepts Myo Munchee on first presentation
2. Tolerates initial examination including taking measurements
3. Agrees to not seek out other medical treatment for their dental or OMD issues
4. Insufficient nasal patency - proxy for enlarged adenoids - unable to complete the Rosenthal test by reaching 20 breaths through nose with mouth closed ([reference](#))

Materials

1. Myo Munchees
 - a. Mini: 1.5 years - 4 years
 - b. Junior: 4 - 8 years
2. OMT materials
 - a. Dusico Balloon
 - b. Tongue depressor
 - c. Veggie straw
3. Dental materials
 - a. iTero: <https://itero.com/en-AU>
 - b. Palatometer - image 3 - [link](#)
 - c. Caliper - <https://www.harborfreight.com/hand-tools/measuring-marking/calipers-micrometer/calipers.html>

Methods

Power Calculation

With n=12 subjects per group (1 control and 3 treatment groups), totaling 48 subjects overall, we will have at least 80% power to detect a LARGE¹ effect size (defined as mean difference relative to pooled standard deviation) of 1.2 or higher between any of the treatment groups and control group. With 6 subjects in the control group and 12 subjects in the treatment group, we will only have a power of 60% to detect an effect size of 1.2 or greater.

To have 80% power to detect a medium ($d=0.6$) effect size between any of the treatment groups and control, we would require n=45 subjects per group.

Method of treatment group allocation

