Linear mixed model with random subject intercept will be used to compare treatment and control groups. Adjustments for demographic and clinical variables will be performed if necessary. The main statistical analysis will be performed using intention-to-treat (ITT) principle with a secondary per-protocol analysis. For the ITT analysis, all subjects with at least baseline measurements will be included, while for the per-protocol analysis, only subjects who did not deviate from the protocols will be included.

All statistical hypothesis testing will be performed using 5% significance level.

Measurements

Clinical Measurements

Dental Measurements

[Videos](#) demonstrations of measurement taking process.

- **Palatal transverse width** - measured at the primary canines (cusp tips) and the lingual surface of the 2nd molars (narrowest distance measured at gingival margins):
 - a. Anterior intercanine measured between the primary canines (cusp tips) - Image 2a of Thilander et al. 2009.

[figure not shown]

Figure. Image taken from Figure 2a of Thilander et al. 2009

- b. Posterior intermolar measurement between the lingual surface of the 2nd molars (narrowest distance measured at gingival margins): Bogue index

JOUR. A. M. A.
DEC. 2, 1922

the width of the maxillary arch
determines whether or not there is room for normal
nasal breathing.

Figure. Image taken from Bogue, E.A. 'The Relations of the Dental Arches to Pathologic Affections of the Nasopharynx'. Amer Med. Assoc., Transactions of Section on Dis. of Childhood, 58:110 (1907).

- **Palatal sagittal depth/length** - measured anteriorly from the incisive papilla perpendicularly to a line connecting and posteriorly along the same line perpendicular to the disto-gingival margins of the 2nd molars (at alveolar crests);
 - a. Posterior depth/length: Figure 3 from Thilander et al. 2009

[figure not shown]

Figure. Image taken from Figure 3a of Thilander et al. 2009

(b) Arch Depth

[figure not shown]

Figure. Image taken from Figure 3b of Thilander et al. 2009

- **Palatal vault height:** measured from the center of the line connecting the disto-gingival margins of the 2nd molars (at alveolar crests) down to the contact with the mid-palatal suture.

Palatal Height

Figure. Image taken from Figure 4 of Thilander et al. 2009

- Any changes to patients usual oral routines

C-GASP questionnaire

This survey collects clinical information on the signs and symptoms associated with breathing disturbances.

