 - i. All groups (including control): 30 minutes
- 3. Week 24 (6 months)
 - g. All groups (including control): 1 hour at CCC-SLP and Dentist, total = 2 hours

Treatment timeline

- 1. Initial treatment consults involve educating patients on protocol - occurs 2 weeks after first measurement and successful eligibility screen
 - a. Myo Munchee ONLY group: 15 minutes
 - b. OMT ONLY group: 30 minutes
 - c. Myo Munchee + OMT group: 30 minutes
- 2. Every 2 weeks until week 10 (T10), 8 weeks after initial treatment appointment:
 - a. Myo Munchee ONLY group: 15 minutes
 - b. OMT ONLY group: 30 minutes
 - c. Myo Munchee + OMT group: 30 minutes
- 3. Every 4 weeks after T10 until week 26 (T26):
 - a. Myo Munchee ONLY group: 15 minutes
 - b. OMT ONLY group: 30 minutes
 - c. Myo Munchee + OMT group: 30 minutes

At home timeline

- 1. The exercises prescribed by the CCC-SLP will need to be completed at home outside of therapy appointments
- 2. The weekly and total time commitment over the 6 months
 - a. Myo Munchee ONLY - 6 days/week
 - i. Weekly: 72 minutes/week
 - ii. Total at home time commitment = 31 hours
 - b. OMT ONLY - 6 days/week
 - i. Weekly: 90 minutes OMT exercises.
 - ii. Total at home time commitment = 39 hours
 - c. Myo Munchee and OMT - 6 days/week
 - i. Weekly: 72 minutes Myo Munchee chewing, 90 minutes OMT exercises.
 - 1. Total = 2 hours, 42 minutes
 - ii. Total at home time commitment = 70 hours

Total Time commitment

Enrolling in the study is a 26-week commitment with variation in time commitments for each group.

- 1. Treatment groups
 - a. **Myo Munchee Only:**
 - i. Initial measurement consultation: 1 hour at dentist and CCC-SLP = 2 hours

- ii. T10 and T26 measurement appointments: 1 hour at dentist and CCC-SLP = 4 hours

- iii. Treatment appointments:

- 1. Before T10: 15 minutes every 2 weeks = 1 hour

- 2. After T10: 15 minutes every 4 weeks = 1 hour

- iv. Commitment outside of appointments: Weekly: 72 minutes/week. Total = 31 hours

- v. Total time commitment: approximately **39 hours**

b. Oral Motor Therapy ONLY:

- i. Initial measurement consultation: 1 hour at dentist and CCC-SLP = 2 hours

- ii. T10 and T26 measurement appointments: 1 hour at dentist and CCC-SLP = 4 hours

- iii. Treatment appointments:

- 1. Before T10: 30 minutes every 2 weeks = 2 hours

- 2. After T10: 30 minutes every 4 weeks = 2 hours

- iv. Commitment outside of appointments:

- 1. Oral Motor Therapy: 90 minutes/week. Total = 39 hours

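### The title promises Myo Munchee compared with OMT, but the sizing and the analysis commit only to treatment versus control

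*Protocol*

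**What the plan says.** - **Title (Protocol Title and General Information):** the trial is "to compare the effects of Myo Munchee therapy and Oral Motor Therapy (OMT) in pediatric patients".
- **Introduction and Hypothesis:** OMT "with, or without, adjunctive intervention with Myo Munchee Therapy (MMT), will result in improved SM, OMD" and the other traits. This claims improvement. It does not claim that one therapy is better than the other.
- **Purpose:** three treatment options are to be evaluated, "either as sole interventions, or as adjunctive intervention strategies".
- **Method of treatment group allocation; Treatment Groups:** four randomized arms of 12: A Myo Munchee only, B OMT only, C both, D control.
- **Power Calculation:** 12 per group gives at least 80% power for an effect size "of 1.2 or higher between any of the treatment groups and control group". For d = 0.6 "between any of the treatment groups and control, we would require n=45 subjects per group".
- **Data Analysis:** "Linear mixed model with random subject intercept will be used to compare treatment and control groups", with testing at the 5% level.

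No section says that A-B or C-B will be estimated or tested.

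**The concern.** The headline question is one active therapy against another. The two places that fix the comparison, the sizing and the analysis sentence, name active against control. The only committed results that bear on the title are therefore two separate verdicts, A against D and B against D.

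A difference in significance is not a significant difference. If A reaches 5% against control and B does not, that is no test of A against B. Under this title, though, it is the result most easily read as Myo Munchee beating OMT. The protocol does not say it will be read that way, but it commits to nothing that would prevent it.

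The same gap affects C-B, the effect of adding Myo Munchee to OMT. The adjunctive wording of the hypothesis and purpose implies that question, but the protocol does not list it as an objective.

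**Working it through.** **Inputs.** From the Power Calculation: 12 per group, four groups, d = 1.2, at least 80% power; 6 v 12 gives 60%; d = 0.6 needs 45 per group. From Data Analysis: 5% level. Two-sided testing is assumed because the protocol does not state sidedness and two-sided t tests reproduce its figures. All d values are in SD units of the analysed outcome.

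**1. Reproduce the plan's figures (two-sample t test, noncentral t).**

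- SE of a 12 v 12 difference = √(1/12 + 1/12) = 0.408 SD.
- Noncentrality at d = 1.2 is 1.2/0.408 = 2.94, which on 22 df gives power 80.2%. Stated: at least 80%.
- 6 v 12 at d = 1.2: 61.6%. Stated: 60%.
- d = 0.6 at 80% power: 44.6, rounded up to 45 per group. Stated: 45.

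The power arithmetic is sound.

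**2. Carry it over to A-B and C-B.** All arms have 12, so the same SE applies. The 95% CI half-width is t(0.975) × 0.408.

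| Variance | df | Detectable d at 80% | Power at d = 1.2 | 95% CI half-width |
|---|---|---|---|---|
| Two arms only | 22 | 1.197 | 0.802 | 2.074 × 0.408 = 0.847 SD |
| Pooled over four arms | 44 | 1.169 | 0.820 | 2.015 × 0.408 = 0.823 SD |

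On 22 df, power for smaller A-B differences is 64.9% at d = 1.0, 46.6% at 0.8, 29.0% at 0.6 and 21.6% at 0.5. If dropout left 10 per arm (an assumption), detectable d would be 1.29 to 1.33 and the half-width 0.91 to 0.94 SD.

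**3. How often would separate verdicts mislead?** Simulation of 1,000,000 trials per setting: four arms of 12, a shared control, no dropout, and A and B truly equal at the stated distance above D. The protocol gives no expected effect for this comparison, so the range 0.6 to 1.2 SD is assumed.

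| A and B above D | 0.6 SD | 0.8 SD | 1.0 SD | 1.2 SD |
|---|---|---|---|---|
| Only A significant v D, pooled variance | 14.0% | 16.3% | 14.7% | 10.3% |
| Only A significant v D, pairwise t | 14.1% | 16.6% | 15.3% | 11.3% |
| Exactly one of A, B significant, pooled | 28.1% | 32.5% | 29.4% | 20.6% |
| Exactly one of A, B significant, pairwise | 28.2% | 33.2% | 30.7% | 22.5% |
| Direct A-B favours A, given only A significant, pooled | 13.2% | 12.3% | 12.1% | 12.9% |
| Same, pairwise | 12.6% | 11.6% | 11.5% | 12.2% |

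A direct two-sided 5% test of A-B wrongly favours A in 2.5% of all trials. The misleading pattern is thus 10.3/2.5 = 4.1 to 16.6/2.5 = 6.6 times as frequent. When it occurs, a direct test would agree in only 11 to 13% of cases.

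These are simple t calculations. The repeated-measures model in Data Analysis may give a different interval width.

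**The case against.** The strongest reply is that the operative text is consistent. Hypothesis, purpose, sizing and analysis all fit treatment versus control, and only the title differs. The title also leaves out the combination and control arms, so it may be shorthand. The analysis sentence excludes no contrast and could be read loosely as comparing all four groups. Listing pairwise contrasts is normally left to a statistical analysis plan. The harm arises only if someone draws an inference the protocol never proposes. The A-B interval would be wide and often inconclusive.

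Much of this stands. The clear mismatch is with the title alone, C-B is only implied, no power figure is wrong, and the misreading is a risk and not a stated plan.

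Two parts do not stand. First, the Power Calculation sets one control group against three treatment groups, which supports the versus-control reading of the analysis sentence. Second, contrast coding can wait for the analysis plan, but the choice of groups to compare cannot: this protocol states it, and what it states does not match its title. An analysis plan that follows the protocol would inherit the mismatch. A wide interval is a reason to report the estimate with its interval and to state the limited power.

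**Conclusion.** The concern holds. The title's question has no committed direct answer, because both the sizing and the analysis sentence name only treatment versus control. With A and B equal and 0.6 to 1.2 SD above control, no dropout and 12 per arm, A alone would be significant against control in roughly 10 to 17% of trials, against 2.5% for a direct test wrongly favouring A.

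This is a mismatch of question and analysis, not a numerical error. The stated 80% power at d = 1.2 is right and carries over to A-B and C-B. It should be corrected because the correction is nearly free and the trial's headline depends on it.

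**What to change.** - **Data Analysis:** state that the same four-arm mixed model will estimate A-B and C-B with 95% CIs at the final measurement visit, alongside A-D, B-D and C-D. The sponsor decides which contrast, if any, is primary.
- **Power Calculation:** add that the 12 v 12 contrasts A-B and C-B have 80% power only at d of about 1.2, so a non-significant A-B is not evidence of equivalence.
- **Visit label:** the Measurement and evaluation timeline calls the last measurement "Week 24 (6 months", while Total Time commitment and the Measurement and Treatment Timeline table put it at T26. These must be reconciled so that the final visit is unambiguous. This is incidental to the main point.
- **Alternative:** if no A-B comparison is intended, align the title with treatment versus control and leave the analysis as it is.

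The cost is wording only, with no new data or patients. The downside is two more contrasts on each of three primary outcomes (2 × 3 = 6 more estimates). Reporting them as estimates, unless the sponsor makes one primary, limits that. It does not settle multiplicity across the three outcomes.

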Body Mass Index

Informed to be collected by patient's pediatrician or family physician and shared with dentist; refer to calculator for ongoing measurements <https://www.cdc.gov/bmi/child-teen-calculator/index.html>

Orofacial Myofunctional Dysfunction Measurements

Refer to 'OMD Measurements' document

Postural Assessment

Postural assessment will be assessed using the PostureCo, Inc. PostureScreen application

<https://www.postureanalysis.com/posturescreen-posture-movement-body-composition-analysis-assessment/>.

Refer to appendix for further details

- Anterior, Posterior and Lateral Translations and Angulations
 - a. Head
 - b. Head weight
 - c. Head-Ankle alignment
 - d. Shoulders
 - e. Hip/Pelvis
 - f. Knee

Ankyloglossia

Functional classification of ankyloglossia

- **TRMR-TIP or % of tongue lift:** and taking into account compensation by holding the floor of the mouth down.
 - Refer to steps in figure 1 study on page 3 - Yoon et al. 2017 ([reference](#))
- **Kotlow classification:** by frenulum position/distance from the tip
 - measuring the length of the ventral surface of the tongue (while in full extension) from the insertion of the lingual frenulum to the tongue tip

Examples of tongue functioning and length measurements using the Quick Tongue Tie Assessment Tool (QTAT): mouth opening with tongue tip to incisive papilla (MOTTIP), maximal interincisal mouth opening (MIO), and Kotlow's free-tongue measurement. Tongue range of motion deficit (TRMD) is defined as the difference between MIO and MOTTIP. Tongue range of motion ratio (TRMR) is defined as the ratio of MOTTIP to MIO

Non-clinical measurements

Sleep Inventory Questionnaire

Refer to www.sleepinventory.com website for more information - <https://www.sleepinventory.com/sdis-r-summary/>

Patient compliance tracking

Once a month, the parent of the patient will fill out a 1-week survey to get compliance of the product usage for that week, there will be 6 of these compliance trackers collected.

Treatment Timeline

Measurement and evaluation timeline

1. Beginning at T-0 (when enrolled in study)
 - a. All groups (including control): 1 hour at CCC-SLP and Dentist, total = 2 hours
2. Week 10 (2 months after starting treatment at week 2 (T2)) measurement and treatment appointment
 - a. At CCC-SLP office

- i. Myo Munchee only group: 60 minutes
- ii. OMT only group: 60 minutes
- iii. Myo Munchee + MFT group: 60 minutes
- iv. Control group: 60 minutes
- b. At Dentist office

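### A mixed model with only a random subject intercept makes the test of baseline-to-final palatal change anti-conservative if children differ in growth or response; the size cannot be fixed from the protocol

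*Protocol*

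**What the plan says.** The Data Analysis section of the protocol names the model and its random-effects structure: "Linear mixed model with random subject intercept will be used to compare treatment and control groups". It allows covariate adjustment where needed, makes intention-to-treat the main analysis, and adds: "All statistical hypothesis testing will be performed using 5% significance level". It names no random slope, residual covariance structure, robust standard error, time coding, group-by-visit term or visit at which the groups are compared.

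The middle measurement is described as "Week 10 (2 months after starting treatment at week 2 (T2)) measurement and treatment appointment". For the end of the study, Total Time commitment refers to "T10 and T26 measurement appointments", and the schedule table also has week 26. The Measurement and evaluation timeline puts the last measurement at week 24. These places need to be reconciled.

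Outcomes and objectives lists three primary outcomes, each an expansion of a palatal dimension (width, depth, vault height), without a time point. The Power Calculation compares one treatment group with control at an "effect size (defined as mean difference relative to pooled standard deviation) of 1.2 or higher between any of the treatment groups and control group" and gives no SD in millimetres.

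**The concern.** A random intercept with independent, constant-variance residuals is the compound-symmetry model. It allows children to differ in level but not in how fast they change, so change over 26 weeks may vary between children no more than change over 10 weeks.

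The design makes that hard to believe. The children are growing. The oral motor exercises are chosen by the clinician for each child. Treatment is done at home, and adherence is tracked by monthly surveys. If true change differs between children, the variance of the long change exceeds what the model allows. The model averages within-child variance over all pairs of visits and applies that average to the baseline-to-final contrast.

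At stake are the p values and confidence intervals for palatal expansion at the end of the study. They would overstate the evidence for treatment relative to the stated 5% level.

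**Working it through.** **1. The plan's own figures.** A two-sample t test at two-sided 5% (the protocol does not state sidedness) gives:
- 12 v 12 at d = 1.2: power 80.2% (stated: at least 80%).
- 6 v 12 at d = 1.2: 61.6% (stated: "we will only have a power of 60% to detect an effect size of 1.2 or greater").
- d = 0.6 at 80% power: 44.6, so 45 per group (stated: "we would require n=45 subjects per group").

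The power section reproduces. It is a two-group calculation with a single SD and says nothing about variances across visits.

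**2. Inputs for the check.** From the protocol: 4 groups of 12, visits at weeks 0, 10 and 26, random intercept only, 5% level. Assumed: complete data, two-sided tests, residual SD σ, and linear child-specific change with slope SD τ per week. Write s = 26τ/σ, the SD of true 26-week change divided by the residual SD. The protocol gives no value for s, so a range is shown.

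**3. Variance of one child's baseline-to-final change.**
- True: 2σ² + 26²τ² = 2σ² + 676τ².
- The mean week is 12, and the sum of squares about it is 144 + 4 + 196 = 344. In a group-by-visit random-intercept fit, the residual mean square, on 44 × 2 = 88 df, has expectation σ² + 344τ²/2. The model therefore takes the change variance as 2σ² + 344τ².
- Since 344/676 = 0.509, model SE / true SE = √[(2 + 0.509s²)/(2 + s²)].
- Actual type I error = 2[1 − Φ(1.96 × SE ratio)].

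| s | True variance/σ² | Model variance/σ² | SE ratio | Type I error |
|---|---|---|---|---|
| 0 | 2.00 | 2.00 | 1.00 | 5.0% |
| 0.5 | 2.25 | 2.13 | 0.97 | 5.7% |
| 1 | 3.00 | 2.51 | 0.91 | 7.3% |
| 2 | 6.00 | 4.04 | 0.82 | 10.8% |
| 3 | 11.00 | 6.58 | 0.77 | 13.0% |
| 5 | 27.00 | 14.72 | 0.74 | 14.8% |
| limit | – | – | 0.71 | 16.2% |

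Simulation (20,000 null trials per setting) agrees: about 7% at s = 1 and 13% at s = 3. Testing the same change with its own variance gives 4.7–5.4%.

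**4. Final visit at week 24.** Almost the same: 7.3% at s = 1 and 13.1% at s = 3.

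**5. Change that plateaus by week 10.** The child-specific pattern is now 0, 1, 1, with sum of squares about its mean 4/9 + 1/9 + 1/9 = 0.667. Here s is the SD of that change over σ, and the SE ratio is √[(2 + 0.667s²)/(2 + s²)]:
- s = 1: √(2.667/3) = 0.94, type I error 6.5%.
- s = 2: √(4.667/6) = 0.88, 8.4%.
- s = 3: √(8/11) = 0.85, 9.5%.

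The week 10 contrast has the same variance here, so it is inflated equally.

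**6. Other contrasts from the same random-intercept model (linear change).**

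| Contrast | s = 1 | s = 3 |
|---|---|---|
| Group-by-time slope | 7.0–7.9% | 13.5–14.0% |
| Baseline-adjusted final visit | 6.2–7.2% | 10.5–11.5% |
| Unadjusted final level | 4.4–8.8% | 6.0–16.2% |

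The unadjusted-level ranges reflect different intercept SDs and intercept-slope correlations. A group effect averaged over all visits stays at 4.6–5.5% throughout.

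**The case against.** **The size is assumed.** This stands. No residual SD or between-child SD of change appears in the protocol, and the palatal ranges in the eligibility criteria are cross-sectional. A reader might infer that the test runs at 7–13%. That follows only if the SD of true change is about 1 to 3 residual SDs. At half a residual SD the error rate is 5.7%, which is hardly a problem.

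**No contrast is named.** This also stands. The text says only that groups will be compared, and a visit-averaged group effect would hold its level. But that average includes the pre-treatment measurement, so it dilutes any effect and does not measure expansion. The contrasts that do measure change are inflated.

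**The residual covariance is open.** A random-intercept model can carry visit-specific residual variances, serial correlation or robust standard errors, and an analysis plan not shown here might add them. The protocol does not exclude this, so the point concerns the model as ordinarily read. It still remains that the one covariance feature the protocol states cannot represent differing change.

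**Week 10.** A reader might infer that the model errs in the opposite direction at week 10 and understates the evidence there. That holds under linear child-specific change but reverses if change is complete by week 10. The documents do not say which course applies, so no claim is made about week 10.

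**Conclusion.** The point holds in conditional form. On its ordinary reading, the stated model gives too small a standard error for baseline-to-final change whenever true change varies between children. Confidence in that direction is high; confidence in any single figure is not. Under linear change, the type I error is about 5.7%, 7%, 11% and 13% at SD ratios of 0.5, 1, 2 and 3. It lies between 5% and about 16% overall, and is lower if change plateaus early.

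These figures rest on independent constant-variance residuals, complete data and a baseline-to-final contrast that the protocol implies but does not state. A reader might also infer that the power statement fails. It does not: its figures reproduce and do not depend on this model.

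**What to change.** In Data Analysis, replace the random-subject-intercept wording with a repeated-measures linear mixed model with visit as a category, group-by-visit terms, an unstructured covariance over the three visits (3 variances and 3 covariances, so 6 parameters on 48 children) and Kenward-Roger degrees of freedom. State that the group contrast at the final visit is the main comparison. Reconcile week 24 with week 26 first, so that the contrast refers to one defined visit.

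A random slope added to the intercept, or a direct baseline-adjusted analysis of the final visit, is an acceptable alternative.

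The cost is a sentence or two. If compound symmetry did hold, the contrast would have about 44 rather than 88 degrees of freedom. The critical value would rise from 1.987 to 2.015, and 2.015/1.987 = 1.014, so intervals would be about 1.4% wider.
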